4.3 Treatment Assignment Procedures

Each participant who meets all eligibility criteria for the Regimen will be randomized to receive either pridopidine 45 mg BID or placebo for approximately 24 weeks of placebo-controlled treatment.

4.4 ECG Monitoring

In addition to the ECG performed at the Master Protocol Screening visit, additional ECG monitoring with stopping and monitoring rules will be completed as described below:

QT Stopping Rules:

- QTcF > 500 ms or
- QTcF > 480 ms AND Δ QTcF > 60 ms from regimen baseline value (pre-dose)
 - The regimen baseline QTcF value is the average of triplicate ECGs collected **pre-dose** during the regimen Screening Visit.
 - For all subsequent visits the Δ QTcF is calculated using the regimen baseline QTcF value (pre-dose), as described above (average triplicate screening QTcF).
 - For Baseline post dose visit only, Δ QTcF is calculated from the initial printout, as the ERT Overread will not be available at the time of the Baseline Visit.
 - For all other ECGs (i.e. Week 4 and Week 24), Δ QTcF should be calculated using the baseline QTcF pre-dose (average triplicate screening QTcF) **from the ERT Overread**.
 - For participants who transition into the OLE, the new baseline QTcF is the average triplicate QTcF collected **pre-dose** during the Week 24 visit.
- If a participant meets either of the above stopping rules, IP must be held and the participant will be asked to return to the clinic after 3-14 days for a follow up ECG.
- If the local ECG reading results at the site match either of the above stopping rules, the IP will be held until the ERT overread report is received. If the ERT overread does not confirm a participant meets the stopping rule above, then the participant can restart the study drug.
- If a participant meets either of the above stopping rules, confirmed by the ERT overread, IP must be discontinued and the participant will be asked to return to the clinic after 3-14 days for a follow up ECG.

QT Monitoring Rule:

- QTcF > 480 ms OR Δ QTcF > 60 ms from regimen baseline value (pre-dose)
 - The regimen baseline QTcF value is the average of triplicate ECGs collected **pre-dose** during the regimen Screening Visit.
 - For all subsequent visits the Δ QTcF is calculated using the regimen baseline QTcF value (pre-dose), as described above (average triplicate screening QTcF).
 - For Baseline post dose visit only, Δ QTcF is calculated from the initial printout, as the ERT Overread will not be available at the time of the Baseline Visit.

Figure 2: ECG Monitoring Flow for Regimen Specific Screening Visit to Assess for Regimen D Eligibility* (before IP administration):

Initial ECG assessment will be done to assess eligibility (Figure 2):

- QTcF will be measured by a mean of 3 (triplicate) 12-lead ECG assessments
 - Three 10-second ECG recordings should be performed, with at least one minute between each recording. QTcF will be automatically calculated by the ECG machine, and will be copied onto source documents. Mean QTcF from the three ECG recordings will be calculated manually. The SI should review and confirm the mean QTcF value.
- If the mean QTcF is >450 ms for men and >470 ms for women, then participant will screen fail and will not be randomized within the regimen.
- For participants on Nuedexta, the Nuedexta dose should be taken within 6 hours before triplicate ECG.

[figure not shown]
[figure not shown]

Figure 3: ECG Monitoring Flow for Regimen Specific Baseline post-dose and Week 4 post-dose Visits*

*For participants on Nuedexta, the Nuedexta dose should be taken within 6 hours before the ECG

QTcF value will be automatically calculated by the ECG machine, and will be copied into source documents (Figure 3):

- QTcF will be measured by a single 12-lead ECG, 1-2 hours post-dose administration.
- If QTcF meets Stopping/Monitoring Rules, then ECG will be repeated twice¹ and the QTcF will be determined by the average of the 3 ECGs.
- If the average QTcF meets Stopping Rules, IP will be held, and a follow-up ECG will be performed as soon as practicable (but at least 2 days after stopping IP) to ensure recovery from QT-prolongation.
- If the average QTcF meets Monitoring Rule for the 1st time, participant will be instructed to continue on IP per-protocol and have a follow up, post-dose ECG after 3-14 days
- If a participant meets the Monitoring Rule for the second time, the participant will be instructed to decrease IP to QD dosing for the remainder of the study.
 - A follow-up ECG should occur 3-14 days after decreasing to QD dosing. If the participant meets the monitoring rule for the 3rd time, the participant must discontinue IP immediately.

¹ Standard ECG procedure for abnormal QTcF readings will be for the ECG to be repeated twice (at least 5 minutes after the 1st ECG, and with an interval of at least 1 minute between each of the 2 additional 10-second recordings), and the mean of the 3 measurements will be used to determine final QTcF.

ECG Monitoring Flow at Week 24 for Participants not Enrolling into the OLE

QTcF will be automatically calculated by the ECG machine, and will be copied into source documents:

- QTcF will be measured by **a single** 12-lead **pre-dose** ECG.
 - For participants taking Nuedexta, the Nuedexta dose should be taken within 6 hours before the ECG
- If QTcF meets Stopping/Monitoring Rules, then ECG will be repeated twice² and the QTcF will be determined by the average of the 3 ECGs.
- If the average QTcF meets Stopping Rules, IP will be stopped, and a follow-up ECG will be performed as soon as practicable (but at least 2 days after stopping IP) to ensure recovery from QT-prolongation.

ECG Monitoring Flow at Week 24 for Participants who choose to Enroll into the OLE

- Baseline QTcF for the purpose of OLE will be measured by **a mean of 3 (triplicate)** 12-lead **pre-dose** ECG assessments
 - Three 10-second ECG recordings should be performed, with at least one minute in between each ECG recording. QTcF will be automatically calculated by the ECG machine, and will be copied onto source documents. Mean QTcF from the three ECG recordings will be calculated manually and used as Baseline pre-dose QTcF for the OLE. The SI should review and confirm the mean QTcF.
- For participants taking Nuedexta, the Nuedexta dose should be taken within 6 hours before the ECG.
- If the mean QTcF is >450 ms for men and >470 ms for women at the Week 24 Visit, then participant will not be eligible to continue into the OLE.
- The OLE IP should then be administered to the participant, and **a single** 10-second ECG should be collected 1-2 hours after administration of the OLE IP.
- If QTcF meets Stopping/Monitoring Rules then ECG will be repeated twice² and the QTcF will be determined by the average of the 3 ECGs.
- If the mean QTcF meets Stopping Rules, IP will be held , and a follow-up ECG will be performed as soon as practicable (but at least 2 days after stopping IP) to ensure recovery from QT-prolongation.
- If the mean QTcF meets Monitoring Rule, participant may continue on IP per-protocol and have another ECG after 3 -14 days.
- If a participant meets the Monitoring Rule for the second time, the participant may decrease to QD dosing for the remainder of the study.
- A follow-up ECG should occur 3-14 days after decreasing to QD dosing. If the participant meets the monitoring rule during this follow-up ECG, the participant must discontinue IP immediately.

² Standard ECG procedure for abnormal QTcF readings will be for the ECG to be repeated twice (at least 5 minutes after the 1st ECG, and with an interval of at least 1 minute between each of the 2 additional 10-second recordings), and the mean of the 3 measurements will be used to determine final QTcF.

5 INVESTIGATIONAL PRODUCT

5.1 Investigational Product Manufacturer

Pridopidine active drug product and matching placebo are manufactured by Teva Pharmaceutical Industries, Ltd or by Apotek Produktion & Laboratorier AB (APL) and will be provided centrally by the Sponsor or subsidiary, or designee.

The investigational product will be oral capsules containing 45 mg of pridopidine and matching placebo capsules (as the control treatment product) identical in appearance.

Pridopidine capsules contain the active ingredient pridopidine and inactive excipients. The excipients are silicified micro crystalline cellulose and magnesium stearate.

The investigational product will be produced and packed in 60 count bottles provided by Apotek Produktion & Laboratorier AB, Sweden.

5.2 Labeling, Packaging, and Resupply

IP will be provided in high-density polyethylene (HDPE) bottles labeled with child resistant caps. All packaging and labeling operations for IP will be performed according to Good Manufacturing Practice for Medicinal Products and the relevant regulatory requirements. Participants will be provided with sufficient IP supplies to cover the period until their next study visit when IP will be dispensed. Each bottle will be labelled with the protocol number, storage information, warning language (i.e., as required by local legislation for investigational drug products), dosing and storage instructions.

5.3 Acquisition, Storage, and Preparation

At each investigational site, the IP will be kept at 15 to 25 °C in a secure, limited-access, controlled storage area. Only authorized personnel will have access to the IP. The study personnel at each site will be responsible for the correct storage and handling of the IP. Each bottle will be labelled with the protocol number, storage information, warning language (i.e., as required by local legislation for IP), dosing and storage instructions.

The Investigator is responsible for recording the receipt and use of all IP supplied, and for ensuring the supervision of the storage and allocation of these supplies. Full accountability will be performed for all used and unused IP.

5.4 Drug Returns and Destruction

At each in person visit the steps outlined in Manual of Procedures must be followed for study drug accountability and compliance, as well as study drug return and destruction.

Prior to study drug destruction, all used and unused IP requires a second accountability verification to be completed by a different study team member, and both verifications should be documented on the study destruction logs. No study drug may be destroyed on-site until written

approval is provided by the study monitoring team. Sites should follow their local drug destruction policies.

5.5 Study Medication/Intervention, Administration, Escalation, and Duration

Participants will take 45 mg capsules of active IP/placebo BID (1 capsule in the morning and 1 capsule in the afternoon, approximately 7 to 10 hours after the morning dose); total daily dose (TDD) of 90 mg. Capsules should be swallowed whole with a drink of water (or other liquid) or swallowed whole with substances of other consistencies as appropriate (e.g. applesauce), and can be taken irrespective of meals. For delivery via gastrostomy tube, the capsule can be opened and the contents diluted in 20-30mL of water and mixed. The prepared solution should be used immediately. Flushing with water is recommended to minimize clogging of the gastrostomy tubing after administration.

All participants receiving study intervention are intended to receive the same fixed-dose regimen, in terms of dose and daily (BID) frequency, according to the study schedule. There will be a titration period leading up to the proposed dose whereby at the baseline visit participants will initiate pridopidine/placebo at 45 mg QD and then increase to 45 mg BID after 2 weeks.

5.6 Justification for Dose

The dosage of pridopidine (45 mg BID) was selected on the basis of three large HD clinical studies (HART, MermaiHD, and PRIDE-HD) and has been shown to be safe and well-tolerated in >1300 participants. Pridopidine 45 mg BID showed potential beneficial clinical effects in the PRIDE-HD study, including potential sustainable effects based on the long-term open-label study, and is therefore anticipated to provide efficacy with low safety and tolerability risks. *In vivo* target engagement was demonstrated by a positron emission tomography (PET) imaging study in humans. At 45 mg BID, pridopidine shows near to complete (~90%) S1R binding (¹⁸F]fluspidine) (Figure 1).

5.7 Dosage Changes

After the 2-week up-titration period, participants who are unable to tolerate a BID schedule will be allowed to stay in the study at the lower dose QD schedule for 1 additional week. After 1 additional week of study intervention on the QD schedule, the dose will be increased to a BID dose schedule. If the participant cannot tolerate the second increase to a BID dose schedule, they will be allowed to continue on QD for the remainder of the study.

If a participant meets the ECG Monitoring Rule for a second time, the participant may decrease to QD dosing for the remainder of the study, as long as the Monitoring Rule is not met for a third time.

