3 RSA DESIGN

This study is a multi-center, randomized, placebo-controlled trial, testing active dose of pridopidine (45mg BID), given orally daily versus placebo. Participants will be randomized 3:1 active: placebo.

The study will consist of a screening/baseline visit, a 2-week double-blind, placebo-controlled up-titration period, a 22-week double-blind, full-dose, placebo-controlled treatment period, and a 28-day safety follow-up period (after the last dose of IP) for those participants who do not enter the Open Label Extension (OLE) period of the study.

After signing informed consent, participants will undergo screening assessments to determine eligibility and eligible participants will be randomly assigned in a 3:1 ratio to 1 of 2 study intervention groups:

- Treatment Arm 1 (active): pridopidine 45 mg orally (PO), BID (total daily dose of 90 mg after two week up-titration period at 45mg PO, QD)
- Treatment Arm 2 (control): matching placebo, PO BID

During the 2 week up-titration period (starting on Day 1), all participants will self-administer 1 capsule of study intervention PO once daily (QD) in the morning. In the full-dose treatment period (starting on Day 14) study intervention will be taken BID, in the morning and in the afternoon (approximately 7-10 hours apart). Participants who complete all scheduled visits will have the option of participating in the OLE period of the study.

Throughout the study, participants will be assessed through on-site clinic visits and telephone calls, as specified in the Schedule of Activities (SoA) table.

For participants who complete all scheduled visits, their final visit will be the Follow-Up Safety Call (28 days after the Week 24 clinic visit), unless participants continue on in the OLE. Participants who discontinue study intervention early will be encouraged to complete all other visits as scheduled for the full course of the study per ITT. For participants who withdraw early from the placebo-controlled period, an in-person Early Termination Visit and a Follow-up Safety Call should be conducted. At the Early Termination Visit the same procedures as described for the Week 24 visit should be conducted. At the Follow-up Safety Call, information on clinical status should be collected.

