5.10 Prohibited Medications

Excluded Medications:

Class	Drugs
Antipsychotics	Clozapine, haloperidol, mesoridazine, thioridazine, pimozide, chlorpromazine, perphenazine, risperidone, zuclopenthixol, and sulpiride.
Antiarrhythmic	Disopyramide, procainamide, flecainide, propafenone, amiodarone, dofetilide, ibutilide, and sotalol
Others	Astemizole, terfenadine, azithromycin, erythromycin, moxifloxacin, pentamidine, sparfloxacin, clarithromycin, chloroquine, halofantrine, bepridil, cisapride, domperidone, droperidol, levomethadyl, sevoflurane, anagrelide, budipine, fluconazole, levofloxacin, lidoflazine, ondansetron, probucol, terodiline, vandetanib, tramadol, tamoxifen, atomoxetine, tolterodine

Participants who use the above medications while enrolled in Regimen D of the HEALEY ALS Platform Trial increase their risk of QT prolongation and torsades. If participants inadvertently use these medications while they are on IP, the Medical Monitor should be notified and a single 12-lead ECG should be collected within 3-14 days of initiating the new prohibited co-medication, or higher dose, to test for QTcF prolongation meeting the Monitoring or Stopping Rules.

If there is a clinical indication for any medication specifically prohibited during the study, the Medical Monitor will be notified and engaged in consultation as to how to address.

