6.1.3 Week 4 Visit

If a participant's visit occurs in the morning, the participant should be instructed not to take the morning dose at home, and the morning dose should be administered in-clinic 1-2 hours prior to the post-dose ECG. If a participant's visit occurs in the afternoon, the participant should be instructed to take the morning dose immediately upon waking in the morning, and the second dose should be administered in-clinic 1-2 hours prior to the post-dose ECG.

These visits will take place on Day 28 ± 7 . The following procedures will be performed for the regimen schedule:

- Administer **single** ECG 1-2 hours **AFTER** IP is administered
 - Note: if the participant is taking Nuedexta, the Nuedexta dose should be taken within 6 hours prior to the ECG. If participant has taken Nuedexta outside of this window, the ECG should still be completed and a protocol deviation recorded. Refer to the MOP for additional guidance.
- Plasma collection **AFTER** ECG
 - All blood samples should be collected after the ECG is performed. If the blood samples cannot be collected after the ECG due to scheduling constraints, blood samples should be collected at least one hour prior to the ECG.
- Voice Recording
- Remind participant to bring study drug to the next visit

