6.1.8 Week 24 Visit or Early Termination Visit

Participants Not Enrolling into the OLE

Only a pre-dose ECG is required at this visit for participant who are not enrolling into the OLE.

If a participant's visit occurs in the morning, the participant should be instructed not to take the morning dose at home, and the morning dose should be administered in-clinic after the pre-dose ECG. If a participant's visit occurs in the afternoon, the participant should be instructed to take the morning dose immediately upon waking in the morning, and the second dose should be taken after the pre-dose ECG.

Participants Enrolling into the OLE

A pre-dose and post-dose ECG are required for participants who enroll into the OLE. The SI should confirm the mean QTcF following the pre-dose triplicate ECG. If the mean QTcF is >450 ms for men and >470 ms for women, then participant will not be eligible to continue into the OLE.

If a participant's visit occurs in the morning, the participant should be instructed not to take the morning dose at home. A pre-dose triplicate ECG should be collected prior to administration of the first dose of OLE IP in-clinic. A single post-dose ECG should then be collected 1-2 hours after administration of the first dose of OLE IP.

If a participant's visit occurs in the afternoon, the participant should be instructed to take the morning dose immediately upon waking in the morning, and a pre-dose triplicate ECG should be collected prior to administration of the first dose of OLE IP in-clinic (which will be the 2nd daily dose).

A single post-dose ECG should then be collected 1-2 hours after administration of the first dose of OLE IP.

This visit will take place on Day 168 ± 7. The following procedures will be performed at either the Week 24 Visit or the Early Termination Visit:

- Home Spirometry
- ALSAQ-40
- CNS-BFS
- CNS-LS
- **Triplicate** ECG monitoring **BEFORE** IP administration
- Administer **single** ECG 1-2 hours **AFTER** IP is administered (only for participants enrolling into the OLE)
 - Note: if the participant is taking Nuedexta, the Nuedexta dose should be taken within 6 hours prior to the pre-dose ECG. If participant has taken Nuedexta outside of this window, the ECG should still be completed and a protocol deviation recorded. Refer to the MOP for additional guidance.
- Plasma PK collection
 - **after** the pre-dose ECG for participants NOT participating in the OLE

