 - **after** the post-dose ECG for participants participating in the OLE
 - All blood samples should be collected after the ECG is performed. If the blood samples cannot be collected after the ECG due to scheduling constraints, blood samples should be collected at least one hour prior to the ECG.
- Voice Recording
- Uninstall Smartphone App
- Dispense IP [See note below.]
- Remind participant to bring investigational product to the next visit (only if continuing in OLE)

Note: Drug is only dispensed at this visit if the participant is continuing in the OLE.

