2.7 Treatment Administration

Pridopidine and placebo are supplied as capsules for oral administration. Each capsule of active study drug contains 45 mg of pridopidine plus silicified microcrystalline cellulose and magnesium stearate as inactive excipients.

The first dose of study drug should be administered while in the office/clinic on the day of the Baseline Visit after all visit assessments are complete except for post-dose ECG recordings.

From the Baseline Visit to the end of Week 2, participants should take one capsule of study drug orally once daily in the morning (the QD dose schedule). Starting at the beginning of Week 3 and throughout the remainder of the study, participants should take one capsule of study drug twice daily, once in the morning and once in the afternoon (approximately 7 to 10 hours after the morning dose; the BID dose schedule).

After the 2-week up-titration period, participants who are unable to tolerate the BID dose schedule should reduce their dosage to the QD dose schedule for one week. If a participant is tolerant of the QD dose schedule, then they should resume the BID dose schedule. If the participant cannot tolerate the second increase to the BID dose schedule, then they should continue on the QD dose schedule for the remainder of the study.

Additional details of treatment administration are described in the RGD RSA.

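### SAP 6.5.14 pools near-trough and near-peak pridopidine concentrations in the Week 24 row (and a few QD values with BID), so the change from Week 4 is not a clean measure of exposure

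*Protocol*

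**What the plan says.** **Sampling.** SAP 5.13 places the PK samples at Week 4 and Week 24. SAP 6.5.14 then summarizes concentrations by treatment group and visit in the regimen-only sample, with no further classification. SAP 4.2 lists change in plasma concentration as an exploratory endpoint.

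**Week 4** (Protocol 6.1.3): "These visits will take place on Day 28 ± 7". A single ECG is done 1-2 hours after dosing and blood is drawn after it. If scheduling prevents that, blood is drawn at least an hour before the ECG. For afternoon visits, "the second dose should be administered in-clinic 1-2 hours prior to the post-dose ECG".

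**Week 24** (Protocol 6.1.8): "Only a pre-dose ECG is required at this visit for participant who are not enrolling into the OLE", and their PK sample follows that ECG. For the others it is drawn after "the post-dose ECG for participants participating in the OLE".

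**Dose schedule.** Protocol 3: "In the full-dose treatment period (starting on Day 14) study intervention will be taken BID". Under Protocol 5.7, a participant who cannot tolerate BID "will be allowed to stay in the study at the lower dose QD schedule for 1 additional week" and then tries BID again. SAP 2.7 words it differently: "participants who are unable to tolerate the BID dose schedule should reduce their dosage to the QD dose schedule for one week". If the second attempt fails, the participant stays on QD. A second ECG Monitoring Rule event also leads to QD for the rest of the study. SAP 6.7.2 summarizes dose reductions and days on reduced dose, but does not link them to the concentrations.

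**The concern.** A concentration can be interpreted only if the time since the last dose and the dosing schedule are known. Here the time since dose differs between the two visits, and within Week 24 it depends on whether the participant chose to enter the OLE. A fall from Week 4 to Week 24 could then appear with no change in clearance, adherence or dose. The Week 24 geometric mean and coefficient of variation would describe a mixture whose composition depends on OLE uptake. The change in concentration is a listed endpoint, and SAP 2.2 also plans to explore how PK relates to pharmacodynamic endpoints, so the mixture could mislead. The stake is descriptive and exploratory only.

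**Working it through.** The plan gives no figure to reproduce, so the sizes below come from a simple model.

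**Inputs from the Protocol.** Half-life about 10 h at steady state (1.1.2); doses 7-10 h apart (5.5); predicted QTcF effect 6.6 ms at 45 mg BID and slope 0.012 ms per ng/mL (1.1.2); mean peak 618 ng/mL (1.1.1).

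**Assumptions.** One compartment, instant absorption, linear superposition, and a non-OLE sample drawn before the in-clinic dose. Protocol 6.1.8 puts both the draw and the dose after the pre-dose ECG and does not state their order.

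**Formulas**, in units of one dose, with gap g hours, half-life h and D = 1 - 2^(-24/h). For h = 10, D = 0.8105.
- BID morning peak = (1 + 2^(-(24-g)/h)) / D
- BID afternoon peak = (1 + 2^(-g/h)) / D
- QD peak = 1/D
- Pre-dose value = peak - 1, so pre-dose/peak = 1 - 1/peak

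**Results, h = 10**

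| Visit | g (h) | BID peak | Pre-dose/peak | QD peak/BID peak |
|---|---|---|---|---|
| Morning | 7 | 1.6135 | 0.380 | 0.765 |
| Morning | 10 | 1.7013 | 0.412 | 0.725 |
| Afternoon | 7 | 1.9932 | 0.498 | 0.619 |
| Afternoon | 10 | 1.8506 | 0.460 | 0.667 |

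The pre-dose/peak ratio is 0.38-0.50. The fold difference is 1/0.498 = 2.0 to 1/0.380 = 2.6.

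**Sensitivity.** The same formulas with h = 8 to 12 give 0.29-0.55. If the post-dose sample is drawn 2 h after dosing rather than at the peak, divide by 2^(-2/10) = 0.871, which gives 0.44-0.57.

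**Effect on the Week 24 row.** OLE uptake is not given, so I assume a share q of active participants is sampled pre-dose. With true exposure unchanged, the Week 24 geometric mean relative to an all-post-dose row is r^q, with r = 0.380 to 0.498:
- q = 10%: 0.908-0.933, an apparent fall of 7-9%
- q = 25%: 0.785-0.840, a fall of 16-21%
- q = 50%: 0.617-0.706, a fall of 29-38%

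**QD at Week 4.** On the SAP 2.7 wording, with BID from Day 14 and a step-back d days later, QD runs from Day 14+d to Day 20+d. A visit on Day V is on QD when V-20 <= d <= V-14. For Day 28 that is d = 8-14; for Day 21 it is d = 1-7. If 5% or 20% of the active arm were on QD (assumed), the Week 4 geometric mean would be multiplied by 0.976-0.987 or 0.909-0.948 (QD/BID ratio to the power 0.05 or 0.20).

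**QTcF.** An ECG on QD instead of BID misses 6.6 x (1 - 0.765) = 1.6 ms to 6.6 x (1 - 0.619) = 2.5 ms. With 0.012 x 618 = 7.4 ms it misses 1.7-2.8 ms.

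**Placebo row.** Placebo participants who enter the OLE are sampled after their first open-label dose, so the Week 24 placebo row can contain real drug concentrations.

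**The case against.** The best defence is that 6.5.14 is a descriptive table. Population PK, which would use dosing and sampling times, is left to a separate plan. Neither that plan nor the Master SAP was supplied, and dose-reduction data are already collected for SAP 6.7.2, so a QD flag could be derived later. This stands as far as it goes: parts may already be covered. But the population PK analysis is optional, and 6.5.14 as written fixes a table in which the rows mix sampling times.

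A reader might infer something stronger: that the QD week leaves participants on BID without a valid safety ECG, because Week 4 could fall on QD and the next scheduled ECG, at Week 24, is pre-dose only for non-OLE participants. The documents do not carry it that far.
- The step-back after some days on BID is SAP 2.7 wording. On matters other than analysis, SAP section 1 gives the regimen appendix (the Protocol here) precedence. Its 5.7 reads more like QD continued to about Day 21, which leaves at most a Day 21 visit affected. Its mention of a second increase gives the SAP reading some support, so overlap is possible but not established.
- No intolerance rate or timing is given.
- The missed 1.6-2.8 ms is small against the 480 and 500 ms limits and the 60 ms change limit in Protocol 4.4, and the Protocol regards even the full 6.6 ms as not clinically meaningful.
- The obvious remedies carry costs. Holding Week 4 back delays the first ECG after titration in people who have just shown intolerance. A Week 8 ECG adds in-clinic dosing and, where that visit is remote, a trip. The nearest model, "a single 12-lead ECG should be collected within 3-14 days of initiating the new prohibited co-medication, or higher dose", concerns co-medication rather than a step in study drug.

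**Conclusion.** The point holds for the PK summary and is a low-cost, optional improvement. The main issue is the Week 24 pooling of pre-dose and post-dose samples, which differ about two- to 2.6-fold under the stated model and which arises from the planned visit procedures even if nobody steps back to QD. QD values pooled with BID are a smaller and rarer problem. The size rests on a 10-hour half-life, linear superposition, instant absorption and a non-OLE draw before the in-clinic dose; other half-lives or later sampling change the ratio but do not remove the contrast. The effect on the Week 24 mean depends on OLE uptake, which is unknown. The primary and hierarchical efficacy analyses are untouched, and the case for changing the ECG schedule is not made.

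**What to change.** In SAP 6.5.14:
1. Summarize active-arm concentrations by sample timing relative to the last dose (pre-dose or post-dose) and by actual schedule on the day (QD or BID).
2. Compare Week 4 with Week 24, including the exploratory change endpoint, only within the same timing and schedule.
3. Take timing from recorded dose and draw times, not from OLE entry alone, because the order of draw and dose is not fixed for non-OLE participants and Protocol 6.1.3 and 6.1.8 allow blood before the ECG. The same flag marks placebo participants sampled after a first open-label dose.

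The cost is one or two analysis flags and some small rows, especially for QD. Participants with a post-dose sample at Week 4 and a pre-dose sample at Week 24 drop out of the like-for-like change. The supplied documents do not say whether dose and draw times are captured; if they are not, the ECG type and OLE status serve as a rough proxy. Anything already covered in the Master SAP or the population PK plan need not be repeated.

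Leave the Week 4 window and the ECG schedule as they are. The afternoon instruction in Protocol 6.1.3 assumes a second daily dose, which a QD participant does not have; one line in the Manual of Procedures would settle that, if it is not already there.
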